8.1.2. German Interim Medical Record Review

A German interim medical record review was conducted in Germany in October 2017. This interim medical record review allowed for the collection of a number of baseline characteristics data. This study had the same methodology as the core study and an almost identical eCRF, capturing demographics, clinical characteristics, disease history, treatment history and palbociclib dosing for patients receiving palbociclib combination treatment in line with the approved indications. However, appropriate sections from the CRF relating to clinical outcomes associated with palbociclib combination were omitted from the interim eCRF (ie, ORR, CRF, progression free rates and survival rates). A further full core medical review will be conducted in Germany in April 2019 in line with the methodology outline in [Section 8.1.1](#).

Figure 1. Study Design Depicting the Proposed Time Frame for the Medical Record Reviews

8.2. Setting

Upon study completion, data will be collected from 13 countries with approximately 15-60 physicians (oncologists/gynecologists)¹ recruited per country. Each physician will complete between 3-14 eCRFs (country and sample size dependent). Data will be collected retrospectively at a single point in time from patient medical records.

Initial screening questions/recruitment criteria will ensure the relevant physicians are selected and all other non-qualifying physicians will be excluded. In addition during physician recruitment a representative geographical split and private/public practice split will be sought where possible to ensure a representative sample.

¹ Breast surgeons/general surgeons/gastro-surgeons may also be included as relevant treaters in Japan.

To be eligible, physicians must have treated or be treating two or more HR+/HER2- ABC/MBC patients who meet the eligibility criteria for the study. This will ensure that recruited physicians will be able to complete the minimum number of eCRFs required to participate in the study. Physicians are recruited by local fieldwork agencies in each market. The recruitment process occurs either via custom lists or a panel approach via telephone or email. In keeping with compliance, physicians must have previously stated their willingness to be contacted to participate in such research. Once physicians have been recruited, they must go back to a specific index date, defined in 8.1, and select the next n number of eligible patient records from patients who have been treated with a palbociclib combination. The consecutive approach to recruitment will be stressed to each participating physician to limit selection bias. Physicians will confirm patient eligibility.

Patient records must meet the following criteria to be eligible for the medical record reviews. They must be female, aged 18 or older and they must have been diagnosed with HR+/HER2- ABC/MBC. Patients must have received palbociclib combination in line with country/locally approved indications. For the core record review, palbociclib and letrozole/aromatase inhibitor must have been initiated a minimum of 6 months prior to date of medical record review, and palbociclib and fulvestrant must have been initiated a minimum of 3 months prior to date of medical record review. This will permit the capture of meaningful clinical outcomes data. For the German interim record review, palbociclib was required to have been initiated a minimum of 3 months prior to data collection regardless of partner therapy.

A full list of the eligibility criteria can be found in 8.2.1.

In order to ensure that sufficient data is captured for each indication, indication quotas will be enforced. This will be determined on a country by country basis.

8.2.1. Inclusion Criteria

Physician inclusion criteria

- Oncologist or gynecologist.²
- Responsible for treating a minimum of ≥ 2 -6 (depending on country) ABC/MBC patients who meet the eligibility criteria.
- Agrees to participate in the study and complete the eCRFs within the data collection period.

² Relevant treaters on a country level will be included.

Patient inclusion criteria:

- Female.
- ≥ 18 years old.
- HR+/HER2- breast cancer diagnosis with confirmed metastatic or advanced disease.
- Received palbociclib plus letrozole/aromatase inhibitor or palbociclib plus fulvestrant in line with the licenced indication(s).
- No prior or current enrolment in an interventional clinical trial for ABC/MBC.
- Minimum of three months of follow up data since palbociclib with fulvestrant initiation, or minimum of six months of follow up data since palbociclib with letrozole/aromatase inhibitor initiation (core medical record review).
- Minimum of three months of follow up data since palbociclib initiation (German interim medical record review only).
- Inoperable or recurrent breast cancer (Japan only).

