Recruited physicians must go back in their records to the specific index date and select the next n number of eligible patient records from patients who have been treated with a palbociclib combination. The 'index date' will be defined as 60 days after the physician first prescribed palbociclib + partner therapy following the availability of specific indication in the market. To be eligible, patients must be female, aged 18 or over, have been diagnosed with HR+/HER2- ABC/MBC and must have received palbociclib combination in line with locally approved indications. For the core study, patients must have initiated palbociclib with fulvestrant a minimum of three months, or palbociclib with letrozole/aromatase inhibitor a minimum of six months prior to data collection.

Variables: The variables assessed in this study will be patient demographics at the time of data collection, clinical characteristics, comorbid conditions, early and advanced breast cancer treatment history, palbociclib treatment patterns including dose changes, clinical outcomes (core medical record review only) and time since deceased (no. of days) if applicable.

Data sources: Patient medical records will be used as the data source.

Study size: For the core study up to approximately 476-486 physicians will be recruited, this will enable data to be collected for approximately 3131 patients. Approximately 30- 40 physicians will be recruited collecting 240-250 eCRFs each in Italy, France, Spain, and the UK. For Belgium and Netherlands, 15 physicians will be recruited collecting 150 and 60 eCRFs per country respectively. Approximately 20 physicians will be recruited in Switzerland collecting 100 eCRFs and 50 physicians recruited in Japan to complete approximately 150 eCRFs. Approximately 20 physicians will be recruited in Portugal collecting 100 eCRFs. For the US study 652 eCRFs were collected from 65 physicians, whilst in Argentina 162 eCRFs were collected from 41 physicians. For the German interim review 42 physicians were recruited with 257 eCRFs completed and for the German core study 35 physicians were recruited completing 251 eCRFs. In Canada, 33 physicians completed 259 eCRFs.

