5. MILESTONES

Milestone	Planned date
Start of core data collection (US and Argentina data collection completed by January 2018)	April 2017
Start of German interim data collection	September 2017
End of German interim data collection	October 2017
Study Report: US and Argentina report	February 2018
Start of data collection – Canada, Germany (core))	June 2019
Start of data collection – Belgium, Italy, UK, Switzerland, Japan	Q4 2019
Start of data collection – France, Spain, Netherlands, Portugal	Q1 2020
Study Report – All Countries (US, Argentina, Canada, France, Germany, Italy, UK, Switzerland, Belgium, Spain, Netherlands, Portugal and Japan)	Q2 2021

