6. RATIONALE AND BACKGROUND

Breast cancer is the most common diagnosed cancer and the most common cause of cancer-related death in females worldwide. There were 1.67 million new cases of breast cancer diagnosed globally in 2012, which equated to 12% of all diagnosed cancers. Out of these new cases 522,000 females died of the disease, which represented 15% of female deaths from cancer in 2012.¹ There is a huge worldwide variation in breast cancer survival rates, ranging from 80% or more in North America, Sweden and Japan to 60% in middle-income countries and as low as 40% in low-income countries.² Breast cancer survival rates have increased over the last 50 years, as relative survival increased from 75.2% in 1975 to 90.6% in 2008.³ The 5 year survival rate for females with stage 0/I breast cancer is near to 100%, compared to that of Stage II and III, which are 93% and 72% respectively. Females who are diagnosed with metastatic or stage IV breast cancer have a much lower 5 year survival rate of 22%.⁴

An increased understanding of breast cancer has enabled enhanced profiling of different disease subtypes. Subtype classification is essential in order to decide on the appropriate treatment regime. Breast tumors are grouped according to the expression of hormone receptors (HR) and human epidermal growth factor receptor 2 (HER2). Overall HR status is the most important biomarker for breast cancer classification, as around 75% of all breast cancer tumors are HR positive (HR+). Tumors that are HR+ grow in response to increased levels of the hormones estrogen and progesterone. HR+ breast tumors are the most favorable, as they respond well to hormone therapies. In contrast HR- breast tumors do not respond well to hormone therapies. These tumors are known to be the most aggressive cancers, in regards to tumor size, grade, stage and patient outcome. HER2 positive (HER2+) breast tumors represent around 15% of all breast tumors. These tumors tend to be more aggressive and faster growing than HER2 negative (HER2-) tumors. HR+/HER2- breast cancer is the most common subtype diagnosed in the US. This subtype accounted for around 73% of diagnosed breast cancer cases in 2010. Around 15-20% of breast tumors do not contain HR or HER2; these are known as triple negative breast cancers.⁵

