8. RESEARCH METHODS

8.1. Study Design

This study will be conducted as a retrospective physician based medical record review of patients who have received palbociclib combination in line with locally approved indications. In some countries data may be collected from patients receiving palbociclib combinations before the local reimbursement date, however patients must still be receiving palbociclib combinations in line with the approved indication. The study will comprise of a medical record review conducted in the **US, Canada, Argentina, Italy, UK, France, Germany, Belgium, Switzerland, Spain, Netherlands, Portugal and Japan**. The study design is outlined in [Figure 1](#). The study has been previously conducted in the US, Argentina, Canada with an additional ‘interim’ record review conducted in Germany (with a minimum of 3 month follow up) whereby no long term clinical outcomes were collected. The core German study is now completed with clinical outcome data.

Data collection will be online via electronic data capture using electronic case report form (eCRF). Eligible physicians will be invited to complete an eCRF for up to between 3-14 patients that meet the study criteria. Each eCRF will take a minimum of 25 minutes to complete. Patient eligibility will be confirmed by treating physicians. In order to allow for a sufficiently long observational window, treating physicians will be asked to go back to a specific point in time, the index date, and sequentially select the medical records of the next ‘n’ patients who meet the inclusion criteria. The ‘index date’ will be defined as 60 days after the physician first prescribed palbociclib + partner therapy following the availability of specific indication in the market (eg, If palbociclib + letrozole was available Feb 1, 2015 in the US and the physician initiated a patient on palbociclib+ letrozole the next day, the index date will be April 2, 2015). The index date will differ for the specific indications/combination partners if approved on different dates.

Study materials (ie, the CRF) will be subject to pilot testing with physicians followed by interviews to discuss the length, feasibility, ease of understanding and use, and the relevance to the objectives.

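### The inclusion lists ask for 3 or 6 months of follow-up data where the text asks only for initiation that long before review; early deaths should be stated to be eligible

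*Protocol*

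**What the plan says.** Both documents word the core-review rule in two ways.

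- **Initiation wording.** The Protocol abstract sets the AI/letrozole rule at "a minimum of six months prior to data collection". Protocol 8.2 says that this combination "must have been initiated a minimum of 6 months prior to date of medical record review", with 3 months for fulvestrant. The SAP 3 text agrees.
- **Follow-up-data wording.** The list in Protocol 8.2.1 requires three months of follow-up data on fulvestrant, "or minimum of six months of follow up data since palbociclib with letrozole/aromatase inhibitor initiation (core medical record review". The SAP 3 list has the same bullet.

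The lists carry weight. Protocol 8.2 states: "A full list of the eligibility criteria can be found in 8.2.1". SAP 4.1 defines the full analysis set by the criteria in SAP 3, which holds both wordings. Eligibility is the physician's call: "Physicians will confirm patient eligibility" (Protocol 8.2), and Protocol 8.8 rules out source data verification. Protocol 8.9 leaves further detail of patient selection to the eCRFs, which are not part of the documents.

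Survival at 1 and 2 years after initiation is a primary objective, where sample size and follow-up allow (Protocol 7). SAP 5.5 measures time to death and PFS from the start of palbociclib. No landmark or delayed-entry analysis is planned.

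**The concern.** A patient who started treatment a year before review and died at month 2 meets the initiation rule. Under the list she can fail, because her record holds only two months of follow-up. Neither document says which outcome is meant.

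If such patients are left out while time zero stays at initiation, everyone analysed has survived to month 3 or 6 by construction. Survival is then too high. So is PFS as defined in SAP 7.2.1, where death is an event; SAP Appendix 1 labels that endpoint exploratory. The primary progression-free proportion counts only documented progression (SAP 5.5), so its direction is not fixed. Living patients lost before the cut-off would also be dropped, which biases survival only if loss is related to prognosis.

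**Working it through.** The documents give no survival, early-death or precision figure for this cohort, so there is nothing to reproduce.

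**Inputs.** Cut-off L = 6 months (AI/letrozole) or 3 months (fulvestrant), from Protocol 8.2.1. Share of initiators dying before L: d = 1%, 3% or 5%. This is an assumption, as is the constant hazard.

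**Survival.** Dropping deaths before L makes the estimate target S(t)/S(L) instead of S(t), with S(L) = 1 − d. Under a constant hazard S(t) = (1 − d)^(t/L). Example, AI/letrozole, d = 5%: S(12) = 0.95² = 0.9025; literal list 0.9025/0.95 = 0.950; rise 4.8 points.

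| Partner | d | 12-month: true → literal list | Rise (points) | 24-month rise (points) |
|---|---|---|---|---|
| AI/letrozole | 1% | 98.0 → 99.0% | 1.0 | 1.0 |
| AI/letrozole | 3% | 94.1 → 97.0% | 2.9 | 2.7 |
| AI/letrozole | 5% | 90.2 → 95.0% | 4.8 | 4.3 |
| Fulvestrant | 1% | 96.1 → 97.0% | 1.0 | 0.9 |
| Fulvestrant | 3% | 88.5 → 91.3% | 2.7 | 2.4 |
| Fulvestrant | 5% | 81.5 → 85.7% | 4.3 | 3.5 |

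These are full-compliance figures. If each physician supplies a fixed number of records, the bias scales roughly with the share of records from literal readers: with half of them, 0.5 × 4.75 = 2.4 points in the AI/letrozole 5% case.

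**Sensitivity to mortality.** The only mortality figure in the documents is background: patients with stage IV disease "have a much lower 5 year survival rate of 22" percent (Protocol 6). As a constant hazard, −ln(0.22)/60 = 0.0252 per month, so S(6) = 0.859, S(3) = 0.927 and S(12) = 0.739. The 12-month rise is then 12.1 points (L = 6) or 5.8 (L = 3). A Weibull curve of shape 2 through the same 22% gives 1.4 and 0.4.

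**Scale.** The biases are specific to the partner drug, so the standard error should be too. With an assumed 125 records per partner in a 250-record country, √(S(1 − S)/125) is 1.25 points at 98% and 2.65 at 90%, before any censoring.

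**PFS at the cut-off.** Using the trial medians in Protocol 6 (24.8 and 10.8 months), S(6) = 0.5^(6/24.8) = 84.6% and S(3) = 0.5^(3/10.8) = 82.5%. The rise S(L) × d/(1 − d) for d = 1/3/5% is 0.9/2.6/4.5 points (AI/letrozole) and 0.8/2.6/4.3 (fulvestrant).

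**Documented-progression proportion.** Let e be the share of early deaths with progression documented first, and p = 1 − S(L) − d(1 − e) the share of all initiators with documented progression by L. The bias is d(e − p)/(1 − d). At d = 5%, going from e = 0 to e = 1, it runs from −0.5 to +4.5 points (AI/letrozole) and from −0.7 to +4.3 (fulvestrant). The sign changes at e = 11% and 13%.

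**Would literal screening show?** Treatment start dates, time since death and time from palbociclib start to death are all collected or derived (SAP 5.2 and 5.5). Every eligible patient started at least L months before review, so each early death could have been recorded. With 125 records, the chance of seeing no early death under correct screening is (1 − d)^125: 28% at d = 1%, 2.2% at 3%, 0.2% at 5%. One country may say little if d is near 1%, so countries that shared a screener should be pooled.

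**The case against.** The strongest reply is that the bullets are shorthand for elapsed time. Protocol 8.1 and SAP 2.1 describe the German interim review as "with a minimum of 3 month follow up", and Protocol 8.2 and SAP 3 state that rule as time since initiation. The Protocol abstract explains lack of follow-up as too little time since approval, and SAP 2.1.1 delays France to allow enough follow-up. The design plainly expects deaths: it records vital status and time since death, and counts death as a PFS event. The wording that physicians actually saw is in an eCRF that the documents do not include.

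Most of this stands, and it makes elapsed time the likelier intent. It does not remove the conflict, because the list is what the Protocol calls complete and no sentence covers early deaths.

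A reader might go further and infer that the plan excludes early deaths, or that a misreading could not be found without source verification. The documents support neither. Intent probably runs the other way, and systematic exclusion would show as an absence of early deaths. Scattered misreading by a few physicians would be harder to see, but would also do less harm.

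**Conclusion.** The inconsistency is real, and reconciling it is a minor to moderate matter of eligibility wording. Under the initiation rule the bias is zero. Under a literal reading by all physicians, the upward direction is certain for survival and for PFS whenever anyone dies before the cut-off; for the documented-progression proportion it is uncertain.

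The size is not known. The range of about 1 to 5 points at 12 months rests on an assumed 1% to 5% early deaths, a constant hazard and universal literal reading. It should not be quoted as an estimate for this study. Nor should the 12-point figure: it takes survival from stage IV diagnosis, not from the start of palbociclib, and depends strongly on the shape of the hazard. It may be tempting to infer that the unequal cut-offs favour one partner drug in the comparison by combination. The documents do not support an ordering, because early mortality under each partner is not given.

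**What to change.** 1. **Reconcile the text.** In Protocol 8.2.1 and the SAP 3 list, replace the core bullet with the rule in Protocol 8.2: AI/letrozole combination initiated at least 6 months, or fulvestrant combination at least 3 months, before the date of record review. Add that patients who died or were lost after initiation remain eligible.
2. **Not yet started.** Use the same wording in the eCRF screener. On the Protocol 5 schedule this covers France, Spain, Netherlands and Portugal: 250 + 250 + 60 + 100 = 660 of 2,874 core records (23%). On the SAP 2.1.1 schedule only France starts after Q4 2019 (250, 9%).
3. **Complete or possibly under way.** US, Argentina, Canada and Germany core are complete (652 + 162 + 259 + 251 = 1,324; 46%). The milestone "Start of data collection – Belgium, Italy, UK, Switzerland, Japan" falls in Q4 2019, the quarter of Protocol v2.0 (150 + 240 + 250 + 100 + 150 = 890; 31%). Check the screener used, and tabulate deaths before month 3 (fulvestrant) and month 6 (AI/letrozole). No such deaths, or implausibly few, would suggest literal screening.
4. **If early deaths were screened out.** Label survival as conditional on reaching month 3 or 6, and flag PFS as possibly biased upward. Do not apply delayed entry to PFS, because it would discard early progressions that were observed.

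The cost is one bullet and one sentence per document, a screener check and one table from data already collected. The downside is that some included patients will have short observed follow-up, which Kaplan-Meier handles.

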8.2.2. Exclusion Criteria

Physician exclusion criteria:

- Qualified less than 2 years ago or more than 35 years ago.
- Participated in observational research for ABC/MBC in the last 3 months.
- Have not prescribed either palbociclib plus fulvestrant or palbociclib plus aromatase inhibitor in line with the licenced indication(s).

8.3. Variables

Table 1. List of Study Variables

Variable	Role	Data source(s)	Operational definition
Patient demographics	Baseline Sub-group identifier	Patient records	Age, ethnicity, weight, height, biomarker status, family history of breast cancer.
Clinical characteristics	Baseline Sub-group identifier	Patient records	Patient status (alive/deceased), time since deceased (no. of days), time since initial BC diagnosis, time since ABC/MBC diagnosis, staging, node status, menopause status. ECOG/Karnofsky functional status, diagnosis for which palbociclib combination was prescribed, sites of metastases, de novo vs. recurrent disease, time from diagnosis palbociclib initiation.
Comorbid conditions	Baseline	Patient records	Comorbid conditions.
Early treatment history	Baseline Sub-group identifier	Patient records	Adjuvant treatments received since breast cancer diagnosis. Time since end of adjuvant treatment. Surgery/radiotherapy/neoadjuvant received.
Advanced treatment history	Baseline Sub-group identifier	Patient records	Treatments and supportive therapies received since metastatic/advanced HR+/HER2-diagnosis. Duration of treatments. Reasons for regimen changes.
Palbociclib combination treatment	Exposure Sub-group identifier	Patient records	Starting dose, duration of treatment, changes in dose, interruptions, cycle delays and discontinuations. Where possible reasons for change in treatment. Line of treatment.
Clinical outcomes (Core medical record review only)	Outcomes	Patient records	Proportion progression free, ORR, CC , PFS, 1-yr and 2-yr survival in all patients and within specific subgroups.

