8.7. Data Analysis

Detailed methodology for summary and statistical analyses of data collected in this study will be documented in a Statistical Analysis Plan (SAP), which will be dated, filed and maintained by the sponsor. The SAP may modify the plans outlined in the protocol; any major modifications of primary endpoint definitions or their analyses would be reflected in a protocol amendment.

All analyses are to be descriptive and so all methods to be used will reflect this descriptive nature. The specific method that will be used depends on type of variable being analysed and those methods are:

- Categorical variables – will be described using:
 - Number of observations (n);
 - Number and percent (%) within each category;
 - Number of missing observations.
- Numeric variables – will be described using:
 - Number of observations (n);
 - Mean and Standard deviation;
 - Minimum, Maximum, Median and 1st and 3rd Quartiles;
 - Number of missing observations.
- Time to event – will be described using:
 - A Kaplan-Meier chart that will visually estimate the distribution of times to some events, eg, progression, and will take into account those patients for which the event has not as yet occurred;
 - 1-yr and 2-yr rates, median or some more appropriate percentiles if the median time is not reached in the sample.

The analyses will be conducted (using the methods above) in a number of phases, as already detailed in the study design section.

1. Non EU countries – all variables (as shown in [Section 8.3](#)) will be described.

2. EU countries – selected variables (all shown in [Section 8.3](#) excluding clinical outcomes) will be described.
3. EU countries - all variables will be described.

Missing data will be excluded on a case by case basis and will not be imputed. This will mean that each table will not necessarily be based on the same number of patients.

Subgroup Analysis

Exploratory stratifications will be conducted to explore differences between line of therapy, demographics, treatments, clinical characteristics, baseline co-morbidities or ‘responders’ and ‘non-responders’ to treatment, however these will be only descriptive in nature. Responders and non-responders will be defined according to the best recorded response to palbociclib treatment.

Sample size permitting, additional stratifications may include:

- Insurance type.
- Eastern Cooperative Oncology Group (ECOG) Performance status.
- Age.
- Menopausal status.
- De novo vs. recurrent disease.

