4.3. Stratifications and Subgroups

Stratifications will be conducted to assess differences in outcomes by line of therapy, demographics, treatments clinical characteristics or ‘responders’ and ‘non-responders’ to treatment, however these will be only descriptive in nature. Responders and non-responders will be defined according to the best recorded response to palbociclib treatment.

For wave 1 countries already conducted (US, Argentina and Germany (interim)) additional stratifications included:

- Disease stage at initial diagnosis (ABC vs mBC);
- Combination partner (AI/letrozole vs fulvestrant);
- Treatment sequence (line of therapy: AI 1st line, fulvestrant 1st – 3rd line);

- Age (up to 65, greater than 65 years);
- Metastases, visceral vs. non-visceral disease.

Additional ad hoc stratifications were completed for the US 2017 analysis, as below:

- Age classification by indication (up to 65, >65);
- ECOG at palbociclib initiation for all patients and by indication;
- Palbociclib starting dose 125 mg vs not 125 mg for all patients and by indication;
- Disease progression with initial control vs without initial control;
- Visceral status (mBC only) by indication;
- Alternative classification of metastases by indication (bone metastases only, visceral disease only, bone and visceral, neither (other)).

For analysis of the wave 2 countries (Germany (core), Canada, UK, Italy, France, Belgium, Switzerland, Japan, Spain, Netherlands and Portugal), the following stratifications are requested (dependent of sample size):

- Combination partner (AI/letrozole vs fulvestrant);
- Treatment sequence (line of therapy: AI 1st line, fulvestrant 1st – 3rd line);
- Age <50, ≥50 years old;
- Age <65, ≥65 years old;
- Age <75, ≥75 years old;
- Starting dose 125 mg vs. non 125 mg.

For clinical outcomes variables only:

- Prior chemotherapy by palbociclib indication (AI/letrozole vs fulvestrant);
- Menopause status (peri- or post- menopausal);
- Disease stage at initial diagnosis (ABC vs mBC).

For treatment patterns variables only, the following stratifications may include:

- Academic vs. community institution.

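### Responder strata for PFS and survival need a landmark, and Protocol Table 1 also allows post-initiation variables and vital status as subgroup identifiers

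*Protocol*

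**What the plan says.** Protocol Table 1 (8.3) assigns one role per row.

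- The palbociclib row has the role "Exposure Sub-group identifier". It mixes items fixed at the start (starting dose, line) with items that arise later: "Starting dose, duration of treatment, changes in dose, interruptions, cycle delays and discontinuations".
- The clinical characteristics row has the role "Baseline Sub-group identifier" and begins "Patient status (alive/deceased), time since deceased (no. of days".
- The outcomes row covers the progression-free proportion, ORR, PFS and "1-yr and 2-yr survival in all patients and within specific subgroups".

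Protocol 8.7 states: "Exploratory stratifications will be conducted to explore differences between line of therapy, demographics, treatments, clinical characteristics, baseline co-morbidities or" responders and non-responders. SAP 4.3 is more direct: "Stratifications will be conducted to assess differences in outcomes by line of therapy, demographics, treatments clinical characteristics", again ending with responders and non-responders. Both define responder status by the best response recorded on palbociclib. SAP 4.3 also lists, among the completed US ad hoc stratifications, progression with versus without initial control.

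SAP 7.2 computes every endpoint overall and by the SAP 4.3 stratification variables, sample size permitting. SAP 7.2.1 sets time zero for PFS at palbociclib initiation. No landmark or time-dependent grouping appears in either document.

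On when stratifiers are measured, the protocol abstract says "The variables assessed in this study will be patient demographics at the time of data collection". SAP 5.2 fixes age at initiation but gives no time point for menopausal status, which is a wave 2 stratifier for outcomes. SAP 5.3 collects performance status both at initiation and currently. Protocol 8.7 lists ECOG without saying which applies, although the US ad hoc list in SAP 4.3 specifies initiation.

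**The concern.** A Kaplan-Meier curve from initiation should be split only by what is known at initiation. If membership of a group depends on a later event, everyone in that group is by definition event-free until it happens, while early progressors fall into the other group. The curves then separate without any effect (immortal time bias).

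Response is such an event. So are dose change, interruption, long duration and discontinuation. Vital status is the outcome itself. The analyses are declared descriptive, so no error rate is affected. But both introductions say the results should help inform treatment decisions, and PFS curves by response or dose change are easily read as effects.

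**Working it through.** The documents state no figure on this point, so there is nothing to reproduce. The check asks how large a difference appears when the stratifier has **no** true effect.

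**Inputs from the documents.** Median PFS 24.8 months (letrozole combination) and 10.8 months (fulvestrant combination), Protocol section 6; the SAP introduction gives 9.2 for the latter. Minimum follow-up 6 months (aromatase inhibitor) and 3 months (fulvestrant), Protocol 8.2.1.

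**Assumptions not in the documents.** Exponential PFS. Follow-up uniform from the minimum to 30 months (3 to 30 for survival). 45% of patients destined to respond, at a time R uniform on 2 to 6 months, if still progression free. Dose change in 20%, 35% or 50% by 6 months (constant hazard), or in the same shares of patients but early (mean 2 months). 1-year survival 80% to 95%.

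**Responder split, in closed form** (ignoring censoring before response). Let λ = ln 2 / median, S = exp(−12λ), and E = [exp(−2λ) − exp(−6λ)] / (4λ), the chance of being progression free at the response time. Then 12-month PFS is S/E in responders and 0.55·S/(1 − 0.45·E) in non-responders.

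- Median 24.8: λ = 0.02795, S = 0.715, E = (0.9456 − 0.8456)/0.1118 = 0.895. Responders 0.715/0.895 = 0.80; non-responders 0.393/0.597 = 0.66. False gap 14 points.
- Median 10.8: λ = 0.06418, S = 0.463, E = (0.8795 − 0.6804)/0.2567 = 0.776. Responders 0.463/0.776 = 0.60; non-responders 0.255/0.651 = 0.39. False gap about 20 points.

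A simulation of 1,000,000 patients per scenario with the censoring above gave 0.80 vs 0.66 and 0.60 vs 0.40. The true value is 0.715 or 0.463 in both groups.

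**Other splits that Table 1 would permit** (same simulation, 12-month PFS, no true effect):

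| Split | Median 24.8 | Median 10.8 |
|---|---|---|
| Dose change ever vs never, constant hazard, 20% by 6 months | 0.87 vs 0.62 | 0.70 vs 0.37 |
| Same, 35% | 0.85 vs 0.53 | 0.66 vs 0.29 |
| Same, 50% | 0.83 vs 0.42 | 0.63 vs 0.21 |
| Dose change, early (mean 2 months) | gap 5–8 points | gap 7–10 points |
| Duration ≥12 vs <12 months, treated until progression | 1.00 vs 0.03 | 1.00 vs 0.003 |
| Ongoing vs discontinued, discontinuation = progression | 1.00 vs 0.30 | 1.00 vs 0.21 |

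For vital status, 1-year survival is 1.00 among the living by construction and 0.31 to 0.35 among the deceased.

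**With a landmark.** Fix dose-change status at month 3 among patients still progression free and in follow-up. Simulated 12-month PFS is then 0.78 vs 0.78 and 0.56 vs 0.56, matching exp(−9λ) = 0.778 and 0.561. The same algebra applies to responder status fixed at a landmark: under no effect both groups have the same conditional survival.

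**The case against.** A reader might infer from Table 1 that PFS and survival *will* be stratified by dose change, duration, discontinuation or vital status. The documents do not support that. The label applies to a mixed row containing starting dose and line, which are proper stratifiers. Neither Protocol 8.7 nor any SAP 4.3 list names the later items; from this row the SAP wave 2 list takes only line and starting dose. SAP 7.2 ties the tables to SAP 4.3. SAP Appendix Table 6 already treats time to death and survival as outcomes. This part of the objection stands: Table 1, with the broad words treatments and clinical characteristics, leaves latitude but does not set a plan.

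A reader might also infer that any dose-change split would show a large false gap. That depends on timing, which the documents do not give; with early changes the gap is 5 to 10 points.

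The responder split could be defended as a way to describe who responds, since the SAP introduction names the characteristics of responders as a gap in knowledge. That use is harmless. But SAP 4.3 says the stratifications assess differences in outcomes, and nothing excludes PFS or survival. For the US initial-control split, the SAP does not say which endpoints were tabulated, so it shows only that such strata have been used.

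Most baseline anchoring is already settled in the SAP (age, comorbidities). The gaps that bear on strata are menopausal status and which ECOG value is used.

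**Conclusion.** The point holds in a limited form. Table 1 permits post-initiation variables and vital status as subgroup identifiers, and both documents plan a responder split without a landmark. If PFS from initiation is shown by that split, about 14 to 20 points of the 12-month difference can be artefact. This rests on the assumed response share and timing, exponential PFS and no true effect. Some of any real difference between responders and non-responders may be genuine, but the planned method cannot separate the two.

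The dose-change range (5–10 points early, 25–42 constant hazard) describes a display that is permitted but not planned. Splits by duration, discontinuation or vital status would be near-tautological. Survival by responder status or dose change would be biased in the same direction, but its size was not calculated.

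**What to change.** 1. In Protocol Table 1, limit the subgroup-identifier role to items fixed at palbociclib initiation (for example starting dose, line, combination partner). Move vital status and time since death to the outcomes role.
2. Add to SAP 4.3: *PFS and survival from initiation are stratified only by variables fixed at palbociclib initiation. Any display by response status, dose change or another post-initiation event uses a landmark (for example, status at a fixed month among patients still progression free and in follow-up) or a time-dependent grouping.* Baseline characteristics may still be described by responder status.
3. State that menopausal status and ECOG used as strata are the values at initiation.

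The cost is wording, plus the loss of naive responder curves. Landmark displays drop patients who progress, die or are censored beforehand. Under the medians above, progression or death before month 3 removes 1 − exp(−3λ) = 8% (24.8) or 18% (10.8); before month 6, 1 − exp(−6λ) = 15% or 32%. A landmark no later than the minimum follow-up for each combination limits losses from short follow-up, but an early one leaves later responders in the non-responder group.
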